### STUDY CALENDAR: ENZALUTAMIDE + TASELISIB (CROSSOVER)

Crossover therapy (taselisib) must begin no later than 21 days after the clinic visit at which progression is determined.

Evaluation a	Treatment period							Post treatment		
	Daily	Cycle 1 (28-days)		Cycle 2 (28-days) b		Additional cycles b		End-of-treatment c	30 day follow-up c	
		Day 1	Day 15	Day 1	Day 15	Day 1	Every 2 cycles from C1D1			
Physical exam/signs and symptoms d		X	X	X	X	X		X		
Vital signs (including oxygen sat)		X	X	X	X	X		X		
ECOG Performance Status		X	X	X	X	X		X		
Blood collection	Clinical laboratory tests e		X	X	X	X		X		
	Fasting plasma glucose f		X	X	X		X	X		
	Circulating tumor DNA		X			X		X		
Tumor assessment CTs, bone scan g							X			
Tumor biopsy (metastatic site) h										
Enzalutamide administration (oral)	X	Oral, once-daily administration, starting Day 1								
Taselisib administration (oral)	X	Oral, once-daily administration								
Pill Diary i	X									
Concomitant medications j		X	X	X	X	X				
Adverse events		X	X	X	X	X			X	

- a Evaluation assessments should be performed prior to administration of IMP unless otherwise indicated. Results should be reviewed by the Investigator prior to the administration of the next dose. All visits should occur within 3 days of scheduled visit unless otherwise noted.
- b Patients may continue with daily dosing of enzalutamide with or without taselisib in the absence of unacceptable toxicities after C2 (or if the toxicity has resolved) and with no clinical evidence of disease progression.
- c The 30-day follow-up assessments should be done 30 (±3 days) days after the last dose of enzalutamide and taselisib. 30 day follow-up can be done by phone or by a clinic visit. Any ongoing toxicities should be documented. Any ongoing serious adverse events will be followed every 3 months until resolution. Any AEs or SAEs considered possibly or probably related to IMP that have not stabilized, returned to baseline, or are considered irreversible will continue to be monitored as per the protocol in Section 7.

- d The physical examination will include measurements of height and weight at screening. Weight will be measured on day 1 of each cycle and at the End-of-treatment visit. Physical examination will include examination of major body systems including neurologic, cardiac, respiratory, gastrointestinal, and skin. Clinically relevant signs and symptoms will be reported as AEs.
- e Clinical laboratory tests will include hematology and serum chemistry panel including white blood cell count, differential, hemoglobin, platelet count, sodium, potassium, chloride, bicarbonate, BUN, creatinine, glucose, calcium, and magnesium, SGOT, SGPT, and total serum bilirubin, albumin, and total protein. Additional tests will be performed when clinically appropriate. In case of Grade 3 or higher abnormal liver function results, additional testing will be done weekly until recovery to baseline value. Labs do not have to be repeated on cycle 1, day 1 if they were done up to 7 days prior to day 1. For all other timepoints, labs can be performed up to 3 days prior to each timepoint indicated in the study calendar.
- f FPG (fasting plasma glucose) will be collected at screening, on Days 1 and 15 of C1, on CXD1 of subsequent cycles, and at the End-of-treatment visit. FPG will also be monitored if patients experience Grade  $\geq 1$  hyperglycemia during the course of the study per the hyperglycemia management guidelines provided in section 7.2 of the protocol. FPG does not have to be repeated on cycle 1, day 1 if it was done up to 7 days prior to day 1. FPG can be obtained up to 3 days prior to each timepoint indicated in the study calendar. The fasting plasma glucose is the same as the serum glucose on the days that the patient is fasting. On the days the patient is getting non-fasting labs, it should be serum glucose only. (see Table 3 under section 7.2.1.5)
- g Tumor assessment should be performed approximately every 2 cycles (up to -5 days) while on study treatment and at End-of-treatment visit if not obtained within the past 6 weeks. Scans should consist of CT scan of the chest, abdomen, and pelvis and a bone scan at baseline. Subsequent scans should consist of CT chest, abdomen and pelvis, and bone scan if bone metastases were present on the baseline studies. At the end of treatment, all scans (baseline and through disease progression) should be sent on a CD to the Vanderbilt Cancer Imaging Support Laboratory for central review and assessment. See Section 10.5 for details and address.
- h Tumor biopsies from a metastatic site will be obtained from patients prior to day 1 (this will be the biopsy obtained at disease progression on the enzalutamide only arm).
- i Pill Diary can be found in the packet of supplemental forms.
- j See Section 6.4.2.

## 1. STUDY DESIGN/SUMMARY

This is an open-label phase Ib/II multiple institution trial that evaluates the safety profile and efficacy of enzalutamide with or without taselisib in patients with androgen receptor positive triple negative metastatic breast cancer (AR+ TN MBC). The phase 1b portion will allow any ER/PR status, provided the patient is HER2 negative. Patients with AR positivity, defined as  $\geq 10\%$  of tumor cell nuclei with immunoreactivity for AR, will receive enzalutamide +/- taselisib. All patients in the phase Ib portion will receive both drugs. Patients in the phase II portion will undergo core biopsy of a metastatic lesion (if reasonably safe) at baseline, at day 14-21, and at the time of progression. If a fresh biopsy is deemed not safe, a paraffin block from a prior biopsy or surgery must be available for enrollment. Standard staging radiology scans will be performed at baseline and every 2 cycles (up to - 5 days) thereafter. Upon progression of disease by RECIST, patients on the enzalutamide only arm will be allowed to crossover to enzalutamide + taselisib. Those on the combination arm will be removed from study. Patients will be screened and enrolled from the oncology practice at the Vanderbilt-Ingram Cancer Center, from participating member centers of the Translational Breast Cancer Research Consortium, and from other approved sites.

## 2. OBJECTIVES

### 2.1 Primary Objectives

#### *Phase Ib*

To determine the safety and tolerability of taselisib given in combination with enzalutamide:

- Assessment of dose limiting toxicities (DLTs) during the first 4 weeks of treatment (cycle 1)
- Determination of the maximally tolerated dose (MTD) of taselisib given in combination with enzalutamide

#### *Phase II*

- To evaluate the efficacy, as measured by clinical benefit rate (CBR), of enzalutamide + taselisib in patients with AR+ TN MBC. CBR is defined as the proportion of patients with a best response of CR, PR, or stable disease (SD)  $\geq 16$  weeks.

### 2.2 Secondary Objectives

- To determine the progression free survival (PFS) of enzalutamide + taselisib in patients with AR+ TN MBC. PFS is defined as the time from cycle 1, day 1 until objective tumor progression.
- To assess the pharmacokinetics (PKs) of taselisib and enzalutamide in patients with AR+ TN MBC

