## 6.6 Cross-over post-progression

Patients who are randomized to enzalutamide alone can crossover to receive enzalutamide + taselisib upon disease progression. Patients who are randomized to enzalutamide alone and who discontinue enzalutamide for toxicity cannot crossover to receive single agent taselisib. However, patients on the enzalutamide + taselisib arm can continue to receive single agent taselisib if they discontinue enzalutamide due to toxicity. Patients who cross over to receive taselisib in combination with enzalutamide will follow the assessments and procedures as outlined in the study calendar. The duration of each cycle will continue to be 28 days and the cycle numbers will "reset" to 1 and will be followed by the "X" suffix (e.g., Cycles 1X, 2X, etc.). Crossover therapy (taselisib) must begin no later than 21 days after the clinic visit at which progression is determined, but can begin as early as C1XD1.

Patients must have labs and procedures performed as outlined in the cross-over study calendar and must meet the values as described in the Inclusion Criteria, prior to receiving taselisib based on assessments and procedures performed within 28 days prior to Day 1 of Cycle 1X. Labs and procedures not included in the cross-over study calendar do not have to be repeated. Patients must also agree to a tumor biopsy, as outlined in the eligibility criteria, prior to initiating taselisib. Patients will receive crossover treatment until progression, intolerable toxicity, or elective withdrawal from the study. Patients who crossover will be evaluated with radiologic assessments every 2 cycles until disease progression.

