### 15.3 Phase II Study

The primary endpoint of the phase II portion is to assess the CBR of enzalutamide + taselisib at 16 weeks. This will be studied using a Simon two-stage design. Because there is sparse data on single agent enzalutamide, we also plan to accrue patients to a single agent enzalutamide arm. Patients will be randomized to the dual therapy vs monotherapy arms using a 3:1 randomization. The coordinating center (VICC) will randomly assign patients to an arm. No direct comparison of the two arms will be conducted. Rather, the monotherapy arm will serve as an informal anchor when interpreting results, and will be especially informative when interpreting many of the secondary analyses.

We have designed the enzalutamide + taselisib arm as a Simon optimal two stage. This design allows for early termination for inefficacy. The antiandrogen bicalutamide, in a prior study with a similar patient population, resulted a CBR of approximately 20%. Thus, for this study, we aim to show an improvement in CBR from 20% to 40%. With a Type I error of 10% and a Type II error of 10%, we will accrue 17 patients in the first stage. After the first 17 patients in the phase II portion have completed 2 cycles and obtained scans, the data will be analyzed. If 4 out of the 17 have a response (CR, PR, or SD), we will expand the study to a total of 37. If, at the end of the trial, there are 11 out of 37 patients with response, we will deem the regimen worthy of further study. If there are 3 or few responses in the first 17 patients, the study will terminate early. If 10 or few responses are seen in the total of 37, the regimen will be deemed unworthy of further study. This study has a 55% probability of stopping early under the null hypothesis. Patients whose disease progresses within 30 days of starting the study without a DLT will be replaced during the phase I portion.

Concurrently, an arm of single agent enzalutimide will be accrued. For every 3 patients randomized to the enzalutamide + taselisib arm, 1 patient will be randomized to the enzalutamide only arm. If the dual therapy arm terminates early due to inefficacy, we will also terminate the monotherapy arm. Thus, this arm will have a minimum of 6 and a maximum of 12 patients. We do not plan to do any formal analysis on this group of patients.

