## 15.6 Analysis of Secondary Endpoints

We will calculate the ORR and corresponding 95% confidence intervals at the dose recommended for phase II. The overall PFS data for the patients at the dose recommended for phase II will be estimated using the Kaplan-Meier method with 95% confidence intervals.

Biopsy analysis will be performed in conjunction with the Pathology and Tissue Informatics Core to assess baseline, therapy-induced changes and status upon progression of the following: proliferation (Ki67), mitosis (mitotic index), apoptosis (cleaved caspase 3 levels by IHC), genomic instability (H2AX by IHC), levels of PTEN by IHC, PI3KCA mutational analysis, HER2 (IHC, FISH) and ER/PR levels (IHC). Levels of MEK [total and phosphorylated ERK1/2 (pERK1/2)] and AKT [phosphorylated AKT, S473 (pAKT)] will be measured by IHC.

RNA-seq will be performed on all biopsies to assign a triple negative subtype, to determine baseline and treatment-induced changes in GE after 5-10 days of therapy and define mutations present in the tumors both at baseline and upon progression of the disease. We expect an enrichment of drug resistance-associated mutations/gene amplifications particularly in tumors that regress and later recur while on therapy. Somatic SNPs and structural variants will be validated by whole exome sequencing (WES) of genomic DNA from the tumor and matched blood. We will validate mutations by targeted capture approaches that allow high-level coverage (greater than 200X) and analysis of clonality. The status of p53, BRCA1/2, PIK3CA, PTEN, INPP4B and other mutations associated with TNBC in the tumor tissue is critical for testing our hypothesis. This genetic information is key for determining the prognostic significance of mutations relative to response of agents being tested and for understanding mutation selection relative to the underlying genetic milieu of each tumor at time of entry into the trial. We anticipate significant opportunity for discovery of novel mutations as well as those arising from selection during resistance to the therapies under investigation. Statistics on the correlative endpoints (tissue assays and MRI scan) will be primarily descriptive. Therefore, these studies are considered to be exploratory and potentially hypothesis-generating.

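### Section 15.6 defines the ORR and PFS set by taselisib dose and not by randomised arm, so phase Ib patients enter, post-crossover data are not ruled out, and the enzalutamide-alone arm has no planned summary

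*Combined protocol and SAP*

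**What the plan says.** All references are to the combined protocol and SAP.

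- **Objective.** Section 2.2 states the PFS aim as "To determine the progression free survival (PFS) of enzalutamide + taselisib in patients with AR+ TN MBC" and runs PFS from cycle 1, day 1 to objective progression. It names a regimen and a population, but no dose or arm. Section 6.3 adds ORR as a secondary objective.
- **Analysis set.** Section 15.6 reads "The overall PFS data for the patients at the dose recommended for phase II will be estimated using the Kaplan-Meier method", and its ORR sentence uses the same dose-based description. Neither sentence names an arm.
- **Phase Ib patients.** Section 15.4 counts phase I patients treated at the recommended dose among those evaluable for phase II. Section 4.1.5 lets HER2-negative patients of any ER/PR status into phase Ib.
- **Crossover.** Section 6.6 says "Patients who are randomized to enzalutamide alone can crossover to receive enzalutamide + taselisib upon disease progression". Cycle numbers restart with an X suffix, and scans continue every two cycles. Section 10.5 sends crossover scans for central review.
- **Enzalutamide-alone arm.** Section 1 says the trial "evaluates the safety profile and efficacy of enzalutamide with or without taselisib". Section 15.3 says this arm "will be especially informative when interpreting many of the secondary analyses". The same section rules out a direct comparison and any formal analysis of the arm.

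**The concern.** Phase II is randomised 3:1, so the natural unit for its ORR and PFS is the randomised arm. A set chosen by dose departs from that in three ways.

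1. It admits patients who were not randomised and may not have triple negative disease, although the objective is restricted to that population.
2. It leaves open what to do with response and progression observed after crossover. Such data will exist, and they come from patients who have already progressed on one of the two drugs.
3. It gives no planned ORR or PFS summary for the arm that is meant to help interpret the secondary results.

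Two analysts following Section 15.6 could therefore report different ORR and PFS figures for the combination from the same data. A reader would also have no stated enzalutamide-alone estimate to set beside them.

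**Working it through.** **1. The plan's own figures reproduce.** Inputs from Section 15.3: null CBR 20%, target 40%; "With a Type I error of 10% and a Type II error of 10%, we will accrue 17 patients in the first stage"; stop at 3 or fewer of 17; success if "there are 11 out of 37 patients with response". Exact binomial results:
- P(X ≤ 3 | n = 17, p = 0.20) = 0.549 (plan: 55%).
- Type I error = 0.0948 (limit 0.10); power at 40% = 0.903 (target 0.90).
- A search over two-stage designs returns this one (3/17, 10/37) as optimal.
- 3:1 allocation: 17/3 = 5.7, so 6; 37/3 = 12.3, so 12. Totals are 17 + 6 = 23 and 37 + 12 = 49, as stated.

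None of these figures depends on the wording of Section 15.6.

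**2. Phase Ib share.** The number treated at the recommended dose is not given. Section 6.2 used cohorts of 3, enlarged to 6 after a DLT, and Section 6.2.2 reports no DLTs. I assume 3, with 6 as the upper end of the range, added to the combination arm:
- full accrual: 3/(37 + 3) = 7.5%; 6/(37 + 6) = 14.0%
- stop at stage 1: 3/(17 + 3) = 15.0%; 6/(17 + 6) = 26.1%

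The documents give no outcome data for these patients, so the direction of any shift is unknown.

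**3. Crossover share, if such data were counted.** With 37 combination patients: 6/(37 + 6) = 14.0%; 12/(37 + 12) = 24.5%. The second figure assumes that every enzalutamide-alone patient crosses over.

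**4. Size of the dilution in that case.** All rates and medians here are assumed; the documents give none for ORR or PFS. Pooled ORR = (37 × p1 + 12 × p2)/49:

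| ORR, randomised combination (p1) | ORR after crossover (p2) | Pooled |
|---|---|---|
| 20% | 10% | 8.6/49 = 17.6% |
| 20% | 0% | 7.4/49 = 15.1% |
| 10% | 5% | 4.3/49 = 8.8% |
| 10% | 0% | 3.7/49 = 7.6% |

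For PFS, assume exponential times. With k crossover patients, the pooled median t solves [37 × 0.5^(t/m1) + k × 0.5^(t/m2)]/(37 + k) = 0.5. Medians are in months:

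| m1 | m2 | k = 6 | k = 12 |
|---|---|---|---|
| 4 | 2 | 3.6 | 3.3 |
| 4 | 3 | 3.8 | 3.7 |
| 6 | 2 | 5.1 | 4.5 |
| 6 | 3 | 5.4 | 5.0 |

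**5. What an enzalutamide-alone summary could show.** Clopper-Pearson 95% intervals: 2/12 gives 2.1% to 48.4%; 0/12 gives 0% to 26.5%; 0/6 gives 0% to 45.9%. For comparison, 7/37 gives 8.0% to 35.2%. The widths are 48.4 − 2.1 = 46.3 points for 2/12 and 35.2 − 8.0 = 27.2 points for 7/37.

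**The case against.** A reader might infer that Section 15.6 puts crossover patients into the combination estimate. The documents do not support that.

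- The dose phrase can be read simply as a filter on the phase Ib cohorts (2, 4, 6 and 8 mg in Section 6.2.1), with no intention of an as-treated analysis.
- Section 2.2 starts PFS at cycle 1, day 1. Crossover cycles are labelled 1X, 2X, and crossover happens only at progression. On that reading the PFS event has already occurred before any taselisib is taken.
- Neither Section 6.6 nor the crossover calendar states a taselisib dose. That crossover patients are at the recommended dose is an inference from Section 6.3 and Table 2.

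A reader might also infer that the enzalutamide-alone arm was overlooked. It was not: Section 15.3 openly declines formal analysis of a 6 to 12 patient arm. The secondary analyses it is meant to inform may be largely the tissue work that fills most of Section 15.6. Section 15.7 assigns every patient a response category and Section 15.5 provides for frequencies, so some response counts may be tabulated anyway.

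These points stand, and they limit the finding to an analysis set that is not fully specified. They do not close the gap. The filter reading itself brings phase Ib patients into ORR and PFS. No sentence says how post-crossover data are handled. Descriptive estimates with intervals would respect both disclaimers in Section 15.3.

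**Conclusion.** The concern holds as a gap in the secondary analysis set. The phase Ib inclusion follows from the text (Sections 15.4 and 15.6 together) and conflicts with the population named in Section 2.2. Its share is 7.5% to 14.0% at full accrual if 3 to 6 such patients are added, and that number is an assumption. The crossover part is only an ambiguity. The 24% share is a ceiling that requires every enzalutamide-alone patient to cross over and be counted. Section 6.6 makes full crossover unlikely: it requires inclusion-level values, agreement to biopsy, a start within 21 days, and no stopping of enzalutamide for toxicity. The shifts in ORR and median PFS illustrate assumed rates and do not predict results. The missing enzalutamide-alone summary is a disclosed choice that fits poorly with the role given to that arm. The two-stage CBR design and its error rates are unaffected. The change is worth making because it is cheap, but it is not a flaw in the primary analysis.

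**What to change.** In Section 15.6:

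1. Estimate ORR and PFS in patients randomised to enzalutamide + taselisib, with PFS from cycle 1, day 1 to first progression.
2. Report phase Ib patients at the recommended dose separately, or in a pooled estimate labelled supplementary, and reconcile this with the evaluability sentence in Section 15.4.
3. For patients randomised to enzalutamide alone, give descriptive CBR and ORR with exact 95% intervals and a Kaplan-Meier PFS estimate, using data up to first progression only.
4. Report response and PFS after crossover separately, with time measured from cycle 1X, day 1.
5. Keep the statement that the arms are not directly compared; add no between-arm test.

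The cost is a few sentences and some descriptive tables from data already being collected, with no extra patients. The combination estimate loses a few phase Ib patients from its denominator (for example 37 in place of 40 if there were 3). The enzalutamide-alone intervals will be wide, and showing them tells the reader how little weight the anchor can bear.

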- l Tumor assessment should be performed approximately every 2 cycles (up to -5 days) while on study treatment and at End-of-treatment visit if not obtained within the past 6 weeks. Scans should consist of CT scan of the chest, abdomen, and pelvis and a bone scan at baseline. Subsequent scans should consist of CT chest, abdomen and pelvis, and bone scan if bone metastases were present on the baseline studies. At the end of treatment, all scans (baseline and through disease progression) should be sent on a CD to the Vanderbilt Cancer Imaging Support Laboratory for central review and assessment. See Section 10.5 for details and address.
- m Archived tumor biopsy specimen: 20 unstained slides of archived biopsy block (unstained slides) or fresh tumor biopsy will be requested at the time of enrollment prior to initiation of treatment.
- n Tumor biopsies will only be performed in the phase II portion. A tumor biopsy from a metastatic site will be obtained from patients prior to day 1, at cycle 2 day 14-21, and upon progression of disease. The third biopsy (at the end of treatment) will not be required for patients who are removed from study for reasons other than disease progression. A patient who undergoes a research biopsy procedure for the purpose of this protocol, and in whom inadequate tissue is obtained, is not obligated to undergo a repeat biopsy.
- o See section 9.1. Required only for patients at Vanderbilt and only in the phase II portion. This should be performed prior to tumor biopsy, if possible. If MRI sub-study is not feasible due to scheduling, MRI weight limits, etc., patients may still continue with the remainder of the study.
- p Subjects on the enzalutamide + taselisib arm should begin enzalutamide on day 1 of cycle 1, and taselisib on day 1 of cycle 2.
- q Pill Diary can be found in the packet of supplemental forms.
- r See Section 6.4.2.
- s Phase II only. Biopsy questionnaire should be filled out by the patient on C3D1. Form can be found in the packet of supplemental forms.
- t The cycle 2 day 8 visit is only needed for patients on the combination of taselisib + enzalutamide. Patients on enzalutamide only do not need a visit on this day.

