## 6.8 Duration of Follow-Up

Participants will be followed for 30 days after the final dose of study drug. The 30 day follow-up can be done by phone or through a clinic visit. Patients who at the treatment completion visit have an ongoing serious adverse event or an adverse event leading to treatment discontinuation will be followed every 3 months until the event resolves, the investigator assesses the event as stable, or the patient is lost to follow-up. Participants will also be followed annually for disease progression by phone, and if necessary, by chart review. If the patient is no longer coming to the institution for care, then the patient may be called as needed for follow-up.

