#### Time point response

Target Lesions	Non-Target Lesions	New Lesions	Overall Response
CR	CR	No	CR
CR	Non CR/Non PD	No	PR
CR	Not evaluated	No	PR
PR	Non PD or not all evaluated	No	PR
SD	Non PD or not all evaluated	No	SD
Not all evaluated	Non PD	No	NE
PD	Any	Yes or no	PD
Any	PD	Yes or no	PD
Any	Any	Yes	PD

CR= complete response, PR= partial response, PD= progressive disease, SD= stable disease, NE= not evaluable.

\*In exceptional circumstances, unequivocal progression in non-target lesions may be accepted as disease progression.

Note: Patients with a global deterioration of health status requiring discontinuation of treatment without objective evidence of disease progression at that time should be reported as “*symptomatic deterioration.*” Every effort should be made to document the objective progression even after discontinuation of treatment.

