#### 11.3.2.1 Death and Immediately Life-Threatening Events

Any death and immediately life-threatening event from any cause while a patient is receiving trial treatment on this protocol or up to 30 days after the last dose of trial treatment, or any death and immediately life-threatening event occurring more than 30 days after trial treatment has ended but which is felt to be treatment related must be reported **within 24 hours of discovery of the event**. All deaths must be reported primarily for the purposes of SAE reporting; however, deaths due unequivocally to progression are not SAEs.

Your local IRB should be notified as per institutional policies and their reporting procedure followed. The completed SAE Reporting Form and Form FDA 3500A should be emailed or faxed to the VICC Coordinating Center **within one working day of discovery of the event**.

VICC Coordinating Center will report all SAEs to the regulatory authorities (FDA) per federal guidelines.

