## 15.5 Reporting

Demographic information such as age and race will be tabulated. Descriptive statistics, including means, medians, standard deviations, and ranges for continuous parameters, as well as percents and frequencies for categorical parameters, will be presented. Investigation for outliers and assumptions for statistical analysis, e.g., normality and homoscedasticity will be made. Adverse medical events will be tabulated. NCI toxicity Grade 3 and Grade 4 laboratory abnormalities will be listed.

All patients who receive any study drugs will be included in the toxicity evaluation. All patients who receive study drugs for at least 4 weeks will be included in the efficacy evaluation (modified intention to treat). Deaths, early progression, and other reasons for drop-out of the study prior to 4 weeks will be reported.

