## 15.7 Reporting and Exclusions

All patients included in the study must be assessed for safety, tolerability, and response to treatment, even if there are major protocol treatment deviations or if they are ineligible. Each patient will be assigned one of the following categories: 1) complete response, 2) partial response, 3) stable disease, 4) progressive disease, 5) early death from malignant disease, 6) early death from toxicity, 7) early death because of other cause, or 9) unknown (not assessable, insufficient data).

All of the patients who met the eligibility criteria and received study drugs for 4 weeks should be included in the main analysis of the clinical benefit rate. Patients in response categories 4-9 should be considered to have a treatment failure (disease progression). Thus, an incorrect treatment schedule or drug administration does not result in exclusion from the analysis of the response and clinical benefit rate.

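### PFS is defined without death as an event, so as written it is time to progression under the PFS label and can read too high

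*Combined protocol and SAP*

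**What the plan says.** Section 2.2 holds the only definition of PFS: "PFS is defined as the time from cycle 1, day 1 until objective tumor progression". Section 6.3 names PFS as a secondary objective without defining it.

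The analysis in Section 15.6 reads: "The overall PFS data for the patients at the dose recommended for phase II will be estimated using the Kaplan-Meier method", with 95% confidence intervals. It lists no events, no censoring rule and no handling of death.

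Other sections bear on deaths and follow-up:

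- Section 15.7 sets up response categories that include early deaths by cause, and then says: "Patients in response categories 4-9 should be considered to have a treatment failure (disease progression". The surrounding sentences concern response and CBR, and PFS is not mentioned.
- Section 15.5 sets the efficacy population: "All patients who receive study drugs for at least 4 weeks will be included in the efficacy evaluation (modified intention to treat".
- Footnote l of the main study calendar schedules scans: "Tumor assessment should be performed approximately every 2 cycles (up to -5 days) while on study treatment". It adds an end-of-treatment scan if none was done in the previous 6 weeks.
- After treatment, Section 6.8 says: "Participants will also be followed annually for disease progression by phone, and if necessary, by chart review". It does not name vital status or date of death.
- Section 11.3.2.1 requires reporting of deaths from any cause "while a patient is receiving trial treatment on this protocol or up to 30 days after the last dose of trial treatment", and of later deaths only if they are thought to be treatment related.
- The note under the response table in Section 10.3.4 asks: "Every effort should be made to document the objective progression even after discontinuation of treatment".

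**The concern.** PFS normally counts death from any cause as an event. An endpoint that counts only progression is time to progression. The two differ whenever a patient dies before progression has been documented.

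Under the current text such a patient has no PFS event. Because no censoring rule is given, the analyst must decide what to do, and the obvious choice in a Kaplan-Meier analysis is to censor. That treats a patient who has died as if progression could still be observed later, and it lifts the curve.

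The plan is also uneven across endpoints. A patient in the efficacy population who dies early is a failure for CBR under Section 15.7 but not an event for PFS under Section 2.2.

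At stake are the reported PFS curve and median, any reading of them beside a PFS that counts deaths, and the exploratory analysis of PIK3CA mutation and PTEN loss on PFS (Section 2.3), which takes over the same definition. Deaths before 4 weeks on drug fall outside the efficacy population and are a separate matter.

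**Working it through.** The plan states no PFS median, rate, event count or sample size, so there is no PFS figure to reproduce. The check has two parts.

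**1. Does any section make death a PFS event?**

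| Section | What it settles | Death as a PFS event? |
|---|---|---|
| 2.2 | Start (cycle 1, day 1) and event (objective progression) | No |
| 6.3 | Names PFS only | No |
| 15.6 | Kaplan-Meier with 95% intervals | Not addressed |
| 15.7 | Early deaths are failures for response and CBR | No; gives no PFS event or event date |
| 11.3.2.1 | Safety reporting of deaths | No |
| 3.3.2.1 | Reports another trial's radiographic PFS as progression or death | Background only |

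None does.

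Death without documented progression is possible in this trial. Scheduled scans stop with treatment apart from the end-of-treatment scan. Patients can leave for toxicity, by their own decision or for non-compliance (Section 6.9), and later contact is annual. A patient can also die on treatment between two scans.

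**2. How large could the effect be?**

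Inputs:

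- n = 37, the full size of the combination arm (Section 15.3).
- f = share of first events that are deaths without documented progression. This is **not in the documents**. It is assumed to be 0%, 5%, 10% or 20%.
- Deaths are censored, and the two cause-specific hazards stay in constant ratio: (1 − f)h for progression and f·h for death.

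True PFS is S = exp(−H), where H is the cumulative hazard of any first event. With deaths censored, the curve estimates exp(−(1 − f)H) = S^(1−f). If the hazards are also constant over time, the median is multiplied by 1/(1 − f).

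| f | True 50% reads | Shift (points) | True 25% reads | Shift (points) | Median multiplied by | Deaths in 37 (37 × f) |
|---|---|---|---|---|---|---|
| 0% | 50.0% | 0 | 25.0% | 0 | 1.000 | 0 |
| 5% | 0.5^0.95 = 51.8% | +1.8 | 0.25^0.95 = 26.8% | +1.8 | 1/0.95 = 1.053 | 1.9 |
| 10% | 0.5^0.90 = 53.6% | +3.6 | 0.25^0.90 = 28.7% | +3.7 | 1/0.90 = 1.111 | 3.7 |
| 20% | 0.5^0.80 = 57.4% | +7.4 | 0.25^0.80 = 33.0% | +8.0 | 1/0.80 = 1.250 | 7.4 |

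The last column supposes that every patient's first event is observed.

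For scale, the half-width of a 95% interval at 50% with n = 37 is 1.96 × √(0.25/37) = 0.161, about 16 points.

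A simulation (n = 37, 4,000 runs for each f, exponential times, assumed true median 3 months) gave typical Kaplan-Meier medians with deaths censored of 3.17, 3.35 and 3.74 months for f = 5%, 10% and 20%. The formula gives 3.16, 3.33 and 3.75. In no run was the deaths-censored median below the median with deaths counted. These figures treat time as continuous. With scans every two 28-day cycles (8 weeks), an observed median would move in coarser steps.

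**The case against.** The strongest reply is that Section 15.7 equates the early-death categories with disease progression, and progression is the PFS event. The background also describes another trial's endpoint as progression or death, so the omission looks like a drafting slip. That may explain how it arose, but it does not repair the rule. Section 15.7 serves response and CBR, covers only deaths it calls early, and supplies no event date. Section 2.2 requires progression to be objective.

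A second reply is that few patients are exposed. Each drug continues until progression or intolerable toxicity. Under Section 6.9, patients who stop one drug may stay on the other with scans every 2 cycles. Section 10.3.4 asks for progression to be documented after treatment stops, and deaths up to 30 days after the last dose are already reported. This stands in part. It narrows the group to patients who stop both drugs or withdraw, and to deaths between scans. It does not remove that group, and a patient who dies unscanned cannot have progression documented afterwards.

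A third reply is that the effect is hypothetical and the stakes are low. The share f is assumed, and even at 20% the shift is under half of the 16-point half-width. The use of 37 is a simplification too, because Section 15.4 adds phase I patients treated at the recommended dose to the phase II evaluable set. PFS is secondary, with no comparison of arms and no decision rule. All of this is correct and limits the importance of the point. It does not make the definition right, and a confidence interval does not show a bias that comes from the definition.

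**Conclusion.** The concern holds. Followed as written, Section 2.2 yields time to progression labelled PFS, and nothing elsewhere corrects it.

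The direction is clear if deaths without documented progression are treated as non-events: the estimate is unchanged or too high. That treatment is inferred, since no censoring rule is stated. The size is unknown, because the documents give no rate for such deaths. The tabulated shifts rest on the assumed f and on proportional cause-specific hazards, and the median factors also need hazards constant over time.

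The primary CBR analysis, the Simon two-stage design and the go/no-go rule do not depend on it. It should be corrected, but it does not threaten the trial's main conclusion.

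**What to change.** **Needed**

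- In Sections 2.2 and 15.6, define PFS as the time from cycle 1, day 1 to objective progression or death from any cause, whichever comes first.
- In Section 15.6, censor patients who are alive and progression-free at their last adequate tumor assessment.
- In Section 6.8, record vital status and date of death at the existing annual phone or chart contact. Section 11.3.2.1 captures deaths from any cause only to 30 days after the last dose, so the new definition could not be applied fully without this item.

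**Advisable**

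- State in advance how a death after a long gap without assessment is handled. One conventional rule censors at the last adequate assessment when death comes more than two scan intervals (2 × 8 = 16 weeks) later, with a sensitivity analysis that counts the death as an event. In the main analysis such a rule turns some deaths back into censored times, so the sensitivity analysis should accompany it.
- If a progression-only measure is wanted, report it separately as time to progression with death as a competing risk.

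The cost is wording in two sections and one data item at a contact already planned. Sample size, visits and treatment do not change. The PFS estimate may be slightly less favourable.
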